5.5 Pharmacokinetic Assessments

Not applicable.

5.6 Biomarker Assessments

Not applicable.

5.7 Outcomes Research Assessments

Quality-of-life data will be measured using the EORTC QLQ-C30 and EQ-5D-3L questionnaires.

The EORTC QLQ C-30 will be collected in order to assess cancer-specific, health-related quality of life. The EORTC QLQ-C30 is one of the most commonly used QoL instruments in oncology studies and has been assessed in previous studies assessing health-related quality of life in patients with melanoma. The EORTC QLQ-C30 is a 30-item instrument comprising six functional scales (physical functioning, cognitive functioning, emotional functioning, social functioning and global quality of life) as well as nine symptom scales (fatigue, pain, nausea/vomiting, dyspnea, insomnia, appetite loss, constipation, diarrhea, and financial difficulties). Except for the overall health status and global quality of life items, responses for all items are 4-point categorical scales ranging from 0 (not at all) to 4 (very much). The overall health status and quality of life responses are 7-point Likert scales.

The EQ-5D-3L comprises 5 dimensions (mobility, self-care, usual activities, pain/discomfort and anxiety) and a visual analog rating scale (VAS).

5.8 Other Assessments

Not applicable.

5.9 Results of Central Assessments

Not applicable. All assessments will be on site.

6 ADVERSE EVENTS

An *Adverse Event (AE)* is defined as any new untoward medical occurrence or worsening of a preexisting medical condition in a clinical investigation subject administered study drug and that does not necessarily have a causal relationship with this treatment. An AE can therefore be any unfavorable and unintended sign (such as an abnormal laboratory finding), symptom, or disease temporally associated with the use of study drug, whether or not considered related to the study drug.

The causal relationship to study drug is determined by a physician and should be used to assess all adverse events (AE). The causal relationship can be one of the following:

Related: There is a reasonable causal relationship between study drug administration and the AE.

Not related: There is not a reasonable causal relationship between study drug administration and the AE.

The term "reasonable causal relationship" means there is evidence to suggest a causal relationship.

Adverse events can be spontaneously reported or elicited during open-ended questioning, examination, or evaluation of a subject. (In order to prevent reporting bias, subjects should not be questioned regarding the specific occurrence of one or more AEs.)

6.1 Serious Adverse Events

A *Serious Adverse Event (SAE)* is any untoward medical occurrence that at any dose:

- results in death
- is life-threatening (defined as an event in which the subject was at risk of death at the time of the event; it does not refer to an event which hypothetically might have caused death if it were more severe)
- requires inpatient hospitalization or causes prolongation of existing hospitalization (see [NOTE](#) below)
- results in persistent or significant disability/incapacity
- is a congenital anomaly/birth defect
- is an important medical event (defined as a medical event(s) that may not be immediately life-threatening or result in death or hospitalization but, based upon appropriate medical and scientific judgment, may jeopardize the subject or may require intervention [eg, medical, surgical] to prevent one of the other serious outcomes listed in the definition above.) Examples

of such events include, but are not limited to, intensive treatment in an emergency room or at home for allergic bronchospasm; blood dyscrasias or convulsions that do not result in hospitalization.) Potential drug induced liver injury (DILI) is also considered an important medical event. (See [Section 6.6](#) for the definition of potential DILI.)

Suspected transmission of an infectious agent (eg, pathogenic or nonpathogenic) via the study drug is an SAE.

Although pregnancy, overdose, cancer, and potential drug induced liver injury (DILI) are not always serious by regulatory definition, these events must be handled as SAEs. (See [Section 6.1.1](#) for reporting pregnancies).

Any component of a study endpoint that is considered related to study therapy (eg, death is an endpoint, if death occurred due to anaphylaxis, anaphylaxis must be reported) should be reported as SAE (see [Section 6.1.1](#) for reporting details).

NOTE:

The following hospitalizations are not considered SAEs in BMS clinical studies:

- a visit to the emergency room or other hospital department < 24 hours, that does not result in admission (unless considered an important medical or life-threatening event)
- elective surgery, planned prior to signing consent
- admissions as per protocol for a planned medical/surgical procedure
- routine health assessment requiring admission for baseline/trending of health status (eg, routine colonoscopy)
- medical/surgical admission other than to remedy ill health and planned prior to entry into the study. Appropriate documentation is required in these cases
- admission encountered for another life circumstance that carries no bearing on health status and requires no medical/surgical intervention (eg, lack of housing, economic inadequacy, caregiver respite, family circumstances, administrative reason).
- Admission for administration of anticancer therapy in the absence of any other SAEs (applies to oncology protocols)

6.1.1 Serious Adverse Event Collection and Reporting

Sections 5.6.1 and 5.6.2 in the Investigator Brochure (IB) represent the Reference Safety Information to determine expectedness of serious adverse events for expedited reporting. Following the subject's written consent to participate in the study, all SAEs, whether related or not related to study drug, must be collected, including those thought to be associated with protocol-specified procedures. All SAEs must be collected that occur during the screening period and within 100 days of discontinuation of dosing (within 30 days of last visit for enrollment/screening failures).

The investigator should report any SAE that occurs after these time periods and that is believed to be related to study drug or protocol-specified procedure.

An SAE report should be completed for any event where doubt exists regarding its seriousness.

If the investigator believes that an SAE is not related to study drug, but is potentially related to the conditions of the study (such as withdrawal of previous therapy or a complication of a study procedure), the relationship should be specified in the narrative section of the SAE Report Form.

SAEs, whether related or not related to study drug, and pregnancies must be reported to BMS (or designee) within 24 hours. SAEs must be recorded on the SAE Report Form; pregnancies on a Pregnancy Surveillance Form (electronic or paper forms). The preferred method for SAE data reporting collection is through the eCRF. The paper SAE/pregnancy surveillance forms are only intended as a back-up option when the eCRF system is not functioning. In this case, the paper forms are to be transmitted via email or confirmed facsimile (fax) transmission to:

SAE Email Address: Refer to Contact Information list.

SAE Facsimile Number: Refer to Contact Information list.

For studies capturing SAEs through electronic data capture (EDC), electronic submission is the required method for reporting. The paper forms should be used and submitted immediately, only in the event the electronic system is unavailable for transmission. When paper forms are used, the original paper forms are to remain on site.

SAE Telephone Contact (required for SAE and pregnancy reporting): Refer to Contact Information list.

If only limited information is initially available, follow-up reports are required. (Note: Follow-up SAE reports should include the same investigator term(s) initially reported.)

If an ongoing SAE changes in its intensity or relationship to study drug or if new information becomes available, a follow-up SAE report should be sent within 24 hours to the BMS (or designee) using the same procedure used for transmitting the initial SAE report.

All SAEs should be followed to resolution or stabilization.

6.2 Nonserious Adverse Events

A *nonserious adverse event* is an AE not classified as serious.

6.2.1 Nonserious Adverse Event Collection and Reporting

The collection of nonserious AE information should begin at initiation of study drug. All nonserious adverse events (not only those deemed to be treatment-related) should be collected continuously during the treatment period and for a minimum of 100 days following the last dose of study treatment.

Nonserious AEs should be followed to resolution or stabilization, or reported as SAEs if they become serious (see [Section 6.1.1](#)). Follow-up is also required for nonserious AEs that cause interruption or discontinuation of study drug and for those present at the end of study treatment as appropriate. All identified nonserious AEs must be recorded and described on the nonserious AE page of the CRF (paper or electronic).

Completion of supplemental CRFs may be requested for AEs and/or laboratory abnormalities that are reported/identified during the course of the study.

6.3 Laboratory Test Result Abnormalities

The following laboratory test result abnormalities should be captured on the nonserious AE CRF page or SAE Report Form (paper or electronic) as appropriate:

- Any laboratory test result that is clinically significant or meets the definition of an SAE
- Any laboratory test result abnormality that required the subject to have study drug discontinued or interrupted
- Any laboratory test result abnormality that required the subject to receive specific corrective therapy.

It is expected that wherever possible, the clinical rather than laboratory term would be used by the reporting investigator (eg, anemia versus low hemoglobin value).

6.4 Pregnancy

If, following initiation of the study drug, it is subsequently discovered that a study subject is pregnant or may have been pregnant at the time of study exposure, including during at least 5 half lives after product administration, the investigator must immediately notify the BMS Medical Monitor/designee of this event and complete and forward a Pregnancy Surveillance Form to BMS Designee within 24 hours and in accordance with SAE reporting procedures described in [Section 6.1.1](#).

In most cases, the study drug will be permanently discontinued in an appropriate manner (eg, dose tapering if necessary for subject safety).

In the rare event that the benefit of continuing study drug is thought to outweigh the risk, after consultation with BMS, the pregnant subject may continue study drug after a thorough discussion of benefits and risk with the subject.

Protocol-required procedures for study discontinuation and follow-up must be performed on the subject unless contraindicated by pregnancy (eg, x-ray studies). Other appropriate pregnancy follow-up procedures should be considered if indicated.

The investigator must immediately notify the BMS (or designee) Medical Monitor of this event and complete and forward a Pregnancy Surveillance Form to BMS (or designee) within 24 hours and in accordance with SAE reporting procedures described in Section 6.1.1.

Follow-up information regarding the course of the pregnancy, including perinatal and neonatal outcome and, where applicable, offspring information must be reported on the Pregnancy Surveillance Form.

Any pregnancy that occurs in a female partner of a male study participant should be reported to BMS. Information on this pregnancy will be collected on the Pregnancy Surveillance Form.

6.5 Overdose

All occurrences of overdose must be reported as SAEs (see Section 6.1.1 for reporting details).

6.6 Potential Drug Induced Liver Injury (DILI)

Wherever possible, timely confirmation of initial liver-related laboratory abnormalities should occur prior to the reporting of a potential DILI event. All occurrences of potential DILIs, meeting the defined criteria, must be reported as SAEs (see [Section 6.1.1](#) for reporting details).

Potential drug induced liver injury is defined as:

1. AT (ALT or AST) elevation > 3 times upper limit of normal (ULN)
AND
2. Total bilirubin > 2 times ULN, without initial findings of cholestasis (elevated serum alkaline phosphatase),
AND
3. No other immediately apparent possible causes of AT elevation and hyperbilirubinemia, including, but not limited to, viral hepatitis, pre-existing chronic or acute liver disease, or the administration of other drug(s) known to be hepatotoxic.

6.7 Other Safety Considerations

Any significant worsening noted during interim or final physical examinations, electrocardiogram, x-ray filming, any other potential safety assessment required or not required by protocol should also be recorded as a nonserious or serious AE, as appropriate, and reported accordingly.

7 DATA MONITORING COMMITTEE AND OTHER EXTERNAL COMMITTEES

The Scientific Steering Committee (SSC) will closely review the safety data throughout the study to evaluate the risk/benefit ratio in general and for the separate prospective cohorts following a predefined Safety Management Plan.

8 STATISTICAL CONSIDERATIONS

The study will include patients with histologically confirmed stage III (unresectable) or stage IV melanoma and progression after prior treatment containing an anti-CTLA-4 monoclonal antibody treated with nivolumab (BMS-936558) at a dose of 3 mg/kg every 2 weeks. Patients will be treated with 3 mg/kg of nivolumab IV every 2 weeks for a maximum of 24 months.

Based on the Performance Status of the patients, there are 2 pre-defined cohorts: Cohort 1, enrolling patients with progression after prior treatment containing an anti-CTLA-4 monoclonal antibody and Performance Status 0-1 (n is at least 640, 85% of the minimum of the 735 screened) and Cohort 2, enrolling patients with progression after prior treatment containing an anti-CTLA-4 monoclonal antibody and Performance Status 2 (n is at the most 160, 85% of the maximum of the 185 screened; a minimum of 50 patients will be enrolled).

A patient who meets the screening criteria will be treated for a maximum of 24 months with safety follow-up at 30 [± 7] and 70-84 [± 7] days from first follow-up visit post-treatment. With an expected screening failure rate of 15%, a maximum total of about 800 patients (640 PS1 and 160 PS2) will be treated.

The number and percentage of patients with high-grade, treatment-related, select adverse events and their characteristics will be reported overall and by subgroups and during and off-treatment. Overall survival is defined as the time between the start of treatment and the date of death due to any cause. A patient who has not died will be censored at last known date alive. OS will be followed up while patients are on the study drug and every 3 months via in-person visits or phone contact after patients discontinue study drug.

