8.1 Sample Size Determination

Currently, there is only little reliable data describing the percentage of patients with melanoma progressing after prior therapy containing treatment with an anti-CTLA-4 monoclonal antibody, presenting with Performance Status 2, and eligible for nivolumab treatment. It is estimated that a minimum of 20% of the potential study population will initially present with PS2. Given that 20% of the 920 patients screened is 185 patients, it is expected that the full complement of 160 patients will be enrolled into the PS2 cohorts and treated.

With an approximate 15% screening failure rate, a cohort of 735 enrolled PS1 patients is projected to a yield 640 treated patients. With $n = 640$ patients, about 3 will experience a rare adverse event with 0.5% true cumulative event rate with a rate estimated within 95% confidence interval (CI) (0.1%-1.4%). Approximately 2 patients with events and a 95% CI of (0%-1.1%) for assumed true event rate of 0.3% are projected.

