5 SAMPLE SIZE AND POWER

Currently, there is only little reliable data describing the percentage of subjects with melanoma progressing after prior therapy containing treatment with an anti-CTLA-4 monoclonal antibody, presenting with Performance Status 2, and eligible for nivolumab treatment. It is estimated that a minimum of 20% of the potential study population will initially present with PS2. Given that approximately 20% of the 920 subjects screened is 185 subjects, it is expected that the full complement of 160 subjects will be enrolled and treated in the PS2 cohort.

With an approximate 15% screening failure rate, a cohort of 735 screened PS1 subjects is projected to yield 640 treated subjects. With $n = 640$ subjects, about 3 will experience a rare adverse event with 0.5% true cumulative event rate with a rate estimated within 95% confidence interval (CI) (0.1%-1.4%). Approximately 2 subjects with events and a 95% CI of (0%-1.1%) for assumed true event rate of 0.3% are projected.

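### Two sample-size figures are wrong as written: 640 and 160 are not 85% of 735 and 185 (about 13% screening failure is implied), and the synopsis confidence interval for 3 events in 640 is too narrow

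*Protocol*

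**What the plan says.** Protocol Section 8 defines Cohort 1 (PS 0-1) by "n is at least 640, 85% of the minimum of the 735 screened" and Cohort 2 (PS 2) by "n is at the most 160, 85% of the maximum of the 185 screened", with a minimum of 50 in Cohort 2. It then gives the total: "With an expected screening failure rate of 15%, a maximum total of about 800 patients (640 PS1 and 160 PS2) will be treated".

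Protocol Section 8.1 repeats the Cohort 1 projection: "With an approximate 15% screening failure rate, a cohort of 735 enrolled PS1 patients is projected to a yield 640 treated patients". It also gives the overall screening number: "Given that 20% of the 920 patients screened is 185 patients". SAP Section 5 has the same projection but a different base: "a cohort of 735 screened PS1 subjects is projected to yield 640 treated subjects". The synopsis also says screened.

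For precision, all three places take n = 640, a true rate of 0.5% and about 3 events. Section 8.1 and SAP Section 5 give a 95% CI of 0.1%-1.4%; the synopsis gives 0.2%-1.1%. For a true rate of 0.3% and about 2 events, all three give 0%-1.1%.

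Table 3.1-1 in the protocol and Table 1 in the SAP show Cohort 1 as N > 735, without saying whether that counts screened or treated patients.

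**The concern.** This is a single-arm estimation trial. Its size is justified by how closely a rare event rate can be estimated in the treated patients, so the treated number and the interval width carry that justification.

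Three things look wrong. Section 8 states outright that 640 and 160 are 85% of the screened numbers, and they are not. The synopsis and the body give different intervals for one scenario, so at least one is wrong, and the synopsis version is the more favourable. The base of the projection also changes from screened to enrolled in Section 8.1. That matters because Protocol Section 4.5 enrols a patient after eligibility is established, when screening failures have already dropped out, whereas SAP Section 6.3 counts as enrolled anyone who consented and was registered.

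**Working it through.** **Inputs.** Screened: 735 (Cohort 1), 185 (Cohort 2), 735 + 185 = 920 in total. Treated: 640, 160, about 800. Screening failure: 15%. All are from Protocol Sections 8 and 8.1; SAP Section 5 repeats them except for the total of about 800.

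**Step 1: treated numbers at 15% failure.** Treated = screened × (1 − 0.15). Implied failure = 1 − treated/screened.

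| | Screened | Stated treated | 85% of screened | Difference | Implied failure |
|---|---|---|---|---|---|
| Cohort 1 | 735 | 640 | 624.75 | about 15 (2.4%) | 12.9% |
| Cohort 2 | 185 | 160 | 157.25 | about 3 (1.7%) | 13.5% |
| Total | 920 | about 800 | 782 | 18 (2.3%) | 13.0% |

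At 13% failure the stated figures do reproduce: 0.87 × 735 = 639, 0.87 × 185 = 161, 0.87 × 920 = 800.

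**Step 2: screened numbers needed at 15% failure.** Screened = treated / 0.85, rounded up: 640/0.85 gives 753, 160/0.85 gives 189, 800/0.85 gives 942. These are 18, 4 and 22 more than stated.

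**Step 3: a likely source.** Multiplying by 1.15 instead of dividing by 0.85 gives 640 × 1.15 = 736, 160 × 1.15 = 184 and 800 × 1.15 = 920. These match the stated screened numbers to within one patient. This is inferred from the match; the documents show no derivation.

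**Step 4: the intervals.** The plan's own figures first, as exact (Clopper-Pearson) 95% intervals:

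- 3/640: 0.10%-1.36%, which rounds to the 0.1%-1.4% in Section 8.1 and SAP Section 5.
- 2/640: 0.04%-1.12%, which rounds to the stated 0%-1.1%.

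So Section 8.1 and SAP Section 5 reproduce with the exact method. The synopsis figure of 0.2%-1.1% does not, and no other common method gives it for 3/640: Wilson 0.16%-1.37%, Wald (lower limit cut at zero) 0%-1.00%, Agresti-Coull 0.09%-1.44%, Jeffreys 0.13%-1.25%.

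**Step 5: does 625 in place of 640 matter for precision?**

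- 3/625: 0.10%-1.40%, still 0.1%-1.4% when rounded.
- 2/625: 0.04%-1.15%, against 0.04%-1.12% at 640. The upper limit would print as 1.2% instead of 1.1%.
- Chance of seeing at least one event, 1 − (1 − p)^n: at p = 0.5%, 95.6% with 625 and 96.0% with 640; at p = 0.3%, 84.7% and 85.4%.

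**Step 6: the stated minimum.** If screening stopped at exactly 735 and each patient failed independently with probability 15%, the number treated would be binomial with mean 624.75, and the chance of reaching 640 would be about 6%.

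**The case against.** The strongest reply is that these are projections. The failure rate is called approximate in the synopsis, Section 8.1 and SAP Section 5, and all three treated figures lie within 3% of the calculated ones. That stands as a reason to treat the point as minor. It does not rescue Section 8, which states the 85% without qualification, and all three pairs miss in the same direction.

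A reader might infer that the stated sample size will not be delivered. The documents do not support that. For Cohort 1, 735 is a minimum, so screening about 18 more patients reaches 640 and nothing in the plan prevents it. For Cohort 2, 160 is a ceiling above a minimum of 50, so 157 is within plan. The total of about 800 is also a maximum, so 782 does not breach it. Enrolment ends by reference to marketing authorisation and availability, not by a screened count.

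A reader might also infer that 640 is both a floor and a ceiling for Cohort 1, because Section 8 sets "a maximum total of about 800 patients (640 PS1 and 160 PS2) will be treated" beside the minimum. There is a consistent reading: with a total cap of about 800, Cohort 1 is 640 when Cohort 2 fills and larger when it does not. The text could say this more plainly, but it does not contradict itself.

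Finally, the synopsis interval is a separate matter from the screening arithmetic, since neither 640 nor 625 patients produce it. That is right. The two are reported together only because they sit in the same sample-size statement and are corrected together.

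**Conclusion.** Two errors stand.

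1. The 85% in Protocol Section 8 is wrong for both cohorts. The stated pairs imply about 13% screening failure. The only limit affected is the Cohort 1 minimum, which would be missed by about 15 patients (2.4%) if exactly 735 were screened and 15% failed. Precision is practically unchanged.
2. The synopsis CI of 0.2%-1.1% is wrong for about 3 events in 640 and conflicts with Section 8.1 and SAP Section 5. It puts the upper limit at 1.1% where 640 patients support 1.4%. This is the clearer of the two, because it overstates what the trial can show about a rare event.

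The change from screened to enrolled in Section 8.1 is a wording inconsistency to settle at the same time.

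Severity is minor: there is no hypothesis test and so no power to lose, and the intervals in Section 8.1 and SAP Section 5 are right for 640. The conclusion assumes exact binomial intervals, which reproduce the plan's own figures, and reads 735, 185 and 920 as screened counts, as Section 8 does.

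**What to change.** - **Synopsis, Sample Size:** replace 0.2%-1.1% with 0.1%-1.4%, to agree with Section 8.1 and SAP Section 5.
- **Synopsis, Protocol Sections 8 and 8.1, SAP Section 5:** preferably keep 640, 160 and about 800 treated, drop the 85%, and state a screening failure rate of about 13%. If 15% is the rate the sponsor expects, either state that about 753, 189 and 942 screened correspond to those treated numbers, or that 735, 185 and 920 screened project to about 625, 157 and 782 treated. The last option lowers the declared Cohort 1 minimum, while the precision statement is built on 640, so it is the least attractive.
- **Protocol Section 8.1:** call the 735 screened, as the synopsis, Section 8 and SAP Section 5 do.

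The cost is wording in the protocol and SAP. The preferred option needs no change to design, analysis or screening numbers. The synopsis becomes slightly less favourable, with an upper limit of 1.4% in place of 1.1%.
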